**Table 1. Schedule of Assessments for Patients Who do not Develop a Hypersensitivity Reaction**

Study Periods	Screening 	Treatment Period				Post-Treatment Follow-up (Patients who discontinued TEGSEDI) 8-weeks (+/- 1 week) 
		Initial Treatment Visit (Month 0) and Every 4 months Visit (+/- 2 weeks) for 12 months		End of Study Visit		
Procedures and Testing	-2 to 0 weeks prior to first study injection	Pre-injection	Post injection 1-hour ± 15 mins 2-hour ± 15 mins 4-hour ± 30 mins 8-hour ± 30 mins 20-30 hours	Pre-injection	Post injection 1-hour ± 15 mins 2-hour ± 15 mins 4-hour ± 30 mins 8-hour ± 30 mins 20-30 hours	Early Termination Visit 
Informed Consent	X					
Demographics	X					
Medical History	X					
Full Physical Examination 	X					
Abbreviated Physical Examination 		X 		X		X X
Height	X					
Weight	X	X 		X		X X
Vital Signs	X	X	X	X	X	X X
Urine Pregnancy Testing	X 	X 		X 		X 
IgE, IgG, IgM		X	X	X	X	X

	Title: Statistical Analysis Plan
	Program Name: "A Phase 4 Safety Study Assessing the Adverse Events Occurring Within 24 Hours of TEGSEDI Administration in Patients with polyneuropathy of Hereditary Transthyretin-mediated Amyloidosis (hATTR-PN)"
	Protocol #: TEG4004
	[REDACTED]
	Version: Final 2.0 Effective Date: 06 October 2023

Inflammatory Markers		X	X	X	X	X	
Samples for Possible Future Testing		X	X	X	X	X	X
ADA		X 		X		X 	
Adverse Events Post Injection at Study Visit			X		X		
Concomitant Medications	X	X		X		X	X

1. The Screening visit and the Month 0 visit can occur on the same day.
2. The Physical Examination and Weight does not need to be completed at the Month 0 study visit if they were performed during Screening.
3. If the patient withdraws from the study, the patient should return for an ET visit within 2 weeks after the decision to withdraw from the study. If the patient discontinues TEGSEDI, they should have an ET visit within 2 weeks of the decision to end treatment and one follow-up visit 8-weeks ( $\pm$  1 week) after their last dose of TEGSEDI. If the ET and the 8 week follow up visit are within 2 weeks of each other, the assessments can be combined.
4. Urine pregnancy testing is only for women of childbearing potential as defined in the protocol.
5. The baseline ADA sample is only drawn at the Month 0 visit.
6. An ADA sample will only be taken at the Early Termination visit if the patient does not have an End of Study visit.
7. Full physical examination to be undertaken at screening and abbreviated physical examination to be undertaken at initial treatment visit, end of study visit, early termination visit and post-treatment follow-up as indicated to assess changes from screening.

**Table 2. Schedule of Assessments for Patients Who Develop a Hypersensitivity Reaction**

	Title: Statistical Analysis Plan				
	Program Name: "A Phase 4 Safety Study Assessing the Adverse Events Occurring Within 24 Hours of TEGSEDI Administration in Patients with polyneuropathy of Hereditary Transthyretin-mediated Amyloidosis (hATTR-PN)"				
	Protocol #: TEG4004				
	Version: Final 2.0 Effective Date: 06 October 2023				

Study Periods	Screening 	Treatment Period			Post-Treatment Follow-up (Patients who discontinued TEGSEDI) 8-weeks (+/- 1 week) 4-month (+/- 2 weeks) 8-month  (+/- 2 weeks) 12-month  (+/- 2 weeks) Post-Treatment visits
		Initial Treatment Visit (Month 0) and Every 4 months Visit (+/- 2 weeks)		Early Termination Visit	
Procedures and Testing	-2 to 0 weeks prior to first study injection	Pre-injection	Post injection 1-hour ± 15 mins 2-hour ± 15 mins 4-hour ± 30 mins 8-hour ± 30 mins 20-30 hours		
Informed Consent	X				
Demographics	X				
Medical History	X				
Full Physical Examination 	X				
Abbreviated Physical Examination 		X 		X	X
Height	X				
Weight	X	X 		X	X
Vital Signs	X	X	X	X	X
Urine Pregnancy Testing	X 	X 		X 	
IgE, IgG, IgM		X	X	X	
Inflammatory Markers		X	X	X	

	Title: Statistical Analysis Plan
	Program Name: "A Phase 4 Safety Study Assessing the Adverse Events Occurring Within 24 Hours of TEGSEDI Administration in Patients with polyneuropathy of Hereditary Transthyretin-mediated Amyloidosis (hATTR-PN)"
	Protocol #: TEG4004
	[REDACTED]
	Version: Final 2.0 Effective Date: 06 October 2023

Samples for Possible Future Testing		X	X	X	X
ADA		X 	X 	X	X 
Adverse Events Post Injection at Study Visit			X		
Concomitant Medications	X	X		X	X

1. The Screening visit and the Month 0 visit can occur on the same day.
2. The Physical Examination and Weight does not need to be completed at the Month 0 study visit if they were performed during Screening.
3. The 8 month and 12 month follow-up visits will occur only if a Milestone for Study End has not been triggered.
4. Urine pregnancy testing is only for women of childbearing potential as defined in the protocol.
5. The baseline ADA sample is only drawn at the Month 0 visit. The ADA sample is only drawn post injection, at the 20-30 hour time point, in the event of a hypersensitivity reaction.
6. A patient who develops a hypersensitivity reaction during the study will have additional blood samples taken for ADA testing on the day of the hypersensitivity reaction at the 20-30 hour time point and again at their Post-Treatment Follow-up visits for 12 months or when a Milestone for Study End has been met, whichever is earliest. All patients who have a hypersensitivity reaction will be followed for a minimum of 4 months.
7. Full physical examination to be undertaken at screening and abbreviated physical examination to be undertaken at initial treatment visit, end of study visit, early termination visit and post-treatment follow-up as indicated to assess changes from screening.

 	
Title: Statistical Analysis Plan
 
Program Name: "A Phase 4 Safety Study Assessing the Adverse Events Occurring Within 24 Hours of TEGSEDI Administration in Patients with polyneuropathy of Hereditary Transthyretin-mediated Amyloidosis (hATTR-PN)"
 
Protocol #: TEG4004
 
[REDACTED]
 
Version: Final 2.0 Effective Date: 06 October 2023

--	---

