#### 9.1.1. Duration of Patient Participation

For patients with hATTR-PN prescribed TEGSEDI who stay on drug for the duration of the study and do not have any hypersensitivity reactions, participation will be a minimum of 12 months and a maximum of 24 months with visits every 4 months. After the first 12 months, visits will continue every 4 months for a maximum of a further 12 months or until one of the Milestones for Study End is triggered (see definition of [Milestones for Study End](#) below).

For patients with hATTR-PN prescribed TEGSEDI who have a hypersensitivity reaction while in the study, participation will be a minimum of 12 months and a maximum of 36 months depending upon when in their study participation the hypersensitivity reaction occurred. This additional duration is due to the additional Post-Treatment Follow-up visits required in response to the hypersensitivity reaction which are a minimum of an additional 4 months and maximum of an additional 12 months based upon when one of the Milestones for Study End is triggered (see definition of [Milestones for Study End](#) and [ADA Testing and Hypersensitivity](#) below).

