#### 9.1.3. ADA Testing and Hypersensitivity

All patients will have a minimum of 2 ADA samples taken. One sample will be taken at the first on-study visit (Month 0) prior to the scheduled dose of TEGSEDI, and the other sample will be taken at the end of the patient's participation in the study prior to the scheduled dose of TEGSEDI if the patient is still on treatment.

Patients who develop a hypersensitivity reaction during the study will have additional blood samples taken for ADA testing on the day of the hypersensitivity reaction at the 20-30 hour time point and again at their Post Treatment Follow-up visits for 12 months or when one of the Milestones for Study End has been met, whichever is earliest. All patients who have a hypersensitivity reaction will be followed for a minimum of 4 months.

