#### **9.1.4. Discontinuation of TEGSEDI**

If a patient discontinues TEGSEDI for a reason other than a hypersensitivity reaction, the patient will have an ET visit as soon as possible after the decision to end treatment and will be followed for 8 weeks after treatment discontinuation for AEs assessments, changes in vital signs and laboratory sampling.

If a patient discontinues TEGSEDI due to hypersensitivity, the patient will undergo an ET visit and an 8-week follow-up visit. He/she will also return for additional ADA testing at 4 months after the hypersensitivity reaction, and then again at 8 months and 12 months after the hypersensitivity reaction, if the study is still ongoing (see definition of [Milestones for Study End](#)).

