#### **9.2.2.1.3. End of Study Visit**

Patients who plan to continue TEGSEDI treatment at the end of the study will complete an End of Study visit. Assessments as in [Section 9.2.2.1.2.](#) will be undertaken and additionally blood for ADA will be taken.

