##### 9.2.4.4. *Discontinuation of Treatment*

A patient may discontinue treatment for any of the following:

- The patient withdraws consent to continue treatment.
- The patient experiences an AE that in the opinion of the investigator necessitates discontinuation of TEGSEDI.
- In the opinion of the investigator, it is in the best interest of the patient that the patient is withdrawn from treatment.
- The patient develops laboratory test abnormalities that meet any of the treatment discontinuation requirements listed in USPI Section 2.4 ([TEGSEDI USPI](#)) and CPM Section 4.2 ([TEGSEDI CPM](#)).

The reason for discontinuation from treatment must be recorded in the eCRF and source documentation.

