## 6 Schedule of Assessments

The study will consist of a Screening/Qualification period, a Treatment period and Post-Treatment Follow-up period as per Table 1 and Table 2.

The Screening/Qualification period is defined as the interval of time from the signing of informed consent until the first on-study dose of TEGSEDI.

The treatment period begins at the time of the first on study TEGSEDI administration and the end of treatment period is defined as follows:

- For patients who complete treatment with TEGSEDI on study, the last observation in the treatment period will be the 20-30 hour post-injection visit of the last administered TEGSEDI dose on study. If the time of the last TEGSEDI dose is missing, or the time of the assessment in question is missing, the assessment will be included in the treatment period if it occurred on the same day or one day subsequent to the last dose of TEGSEDI
- For patients who discontinue TEGSEDI or withdraw from the study and continue with TEGSEDI outside the study, the early termination (ET) visit will serve as the end of the treatment period

For patients who discontinue TEGSEDI, the post treatment follow-up period begins after the end of the treatment period, as defined above, and ends with the last available data collected per the clinical trial protocol. Data for the post-treatment follow-up period will be analyzed and summarized separately for patients who develop a hypersensitivity reaction.

	Title: Statistical Analysis Plan				
	Program Name: "A Phase 4 Safety Study Assessing the Adverse Events Occurring Within 24 Hours of TEGSEDI Administration in Patients with polyneuropathy of Hereditary Transthyretin-mediated Amyloidosis (hATTR-PN)"				
	Protocol #: TEG4004				
	[REDACTED]				
	Version: Final 2.0 Effective Date: 06 October 2023				

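### Post-reaction follow-up and ADA sampling are promised to every hypersensitivity reactor, but the visits that carry them are scheduled only for reactors who stop TEGSEDI

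*Combined protocol and SAP*

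**What the plan says.** **The duty covers all reactors.** Protocol 9.1.3 states: "All patients who have a hypersensitivity reaction will be followed for a minimum of 4 months". Protocol 9.2.2.1.5 and note 6 to Table 2 repeat this. Protocol 9.1.1 speaks of "additional Post-Treatment Follow-up visits required in response to the hypersensitivity reaction", as if the reaction itself triggered them. After the 20-30 hour sample, note 6 calls for ADA "again at their Post-Treatment Follow-up visits for 12 months or when a Milestone for Study End has been met, whichever is earliest". Protocol 9.2.3.2 says the same for reactions within 24 hours of a study-visit dose.

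**The visits are for those who stop.** The follow-up columns of Table 2 (8 weeks, 4, 8 and 12 months) are headed "Post-Treatment Follow-up (Patients who discontinued TEGSEDI" in both documents. SAP section 6 is equally specific: "For patients who discontinue TEGSEDI, the post treatment follow-up period begins after the end of the treatment period".

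**Stopping is conditional.** Protocol 9.1.4 opens with a condition: "If a patient discontinues TEGSEDI due to hypersensitivity, the patient will undergo an ET visit and an 8-week follow-up visit". Protocol 9.2.4.4 lists reasons for which treatment may be stopped. Hypersensitivity is not named, and the nearest item is: "The patient experiences an AE that in the opinion of the investigator necessitates discontinuation of TEGSEDI". The action codes in 11.4.3.3 include no change to dosing, and interruption followed by restart.

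**ADA while on treatment.** Note 5 to Table 2 limits pre-injection ADA to Month 0. Protocol 9.1.3 and 9.2.3.2 add one sample at the end of participation for everyone. For patients staying on drug, 9.2.2.1.3 says: "Patients who plan to continue TEGSEDI treatment at the end of the study will complete an End of Study visit". That visit includes a dose. SAP Table 2, as supplied, has an Early Termination column but none for End of Study.

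**The concern.** A reactor who remains on TEGSEDI falls under the promise but outside the column that delivers it. Followed literally, the schedule makes ADA sampling after a reaction depend on a treatment decision taken after that reaction.

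The study objective includes subsequent adverse outcomes, and SAP 8.2.2 (risk factors) and 8.2.8 summarise hypersensitivity reactions by ADA status (yes/no). The SAP text does not say which samples determine that status. If any positive sample counts (an assumption), reactors who stop have more chances to be classed as positive than reactors who continue. Patients who continue are also the ones who show what follows re-exposure. For a reaction at the final study dose, the schedule can miss the protocol's own 4-month minimum.

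**Working it through.** The plan gives no figure on this point, so the check is an enumeration of the visit calendar.

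**Inputs**
- Treatment visits every 4 months (protocol 9.1.1; SAP Table 2, with a window of 2 weeks either side).
- Last visit at Month 12 or Month 24, the limits in protocol 9.1.1 for patients without a reaction who stay on drug. SAP Table 1 now shows 12 months.
- The reaction follows a study-visit dose at Month r, and the patient continues TEGSEDI.
- Post-reaction ADA available to that patient: the 20-30 hour sample and the last-visit sample.

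**Formulas.** With last visit L, scheduled follow-up after the reaction is L − r months. The last-visit ADA sample also falls L − r months after the reaction. It is drawn before the injection, so when r = L it precedes the reaction and gives no post-reaction information.

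| Last visit L | Reaction at r | L − r (months) | 4-month minimum met? | Which of 4, 8, 12 months has ADA |
|---|---|---|---|---|
| 12 | 0 | 12 | yes | 12 |
| 12 | 4 | 8 | yes | 8 |
| 12 | 8 | 4 | yes | 4 |
| 12 | 12 | 0 | **no** | none |
| 24 | 0 | 24 | yes | none |
| 24 | 4 | 20 | yes | none |
| 24 | 8 | 16 | yes | none |
| 24 | 12 | 12 | yes | 12 |
| 24 | 16 | 8 | yes | 8 |
| 24 | 20 | 4 | yes | 4 |
| 24 | 24 | 0 | **no** | none |

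**Visit windows.** Where L − r = 4, a reaction visit held 2 weeks late and a last visit held 2 weeks early leave 2 + 2 = 4 weeks less than 4 months, if windows run from nominal dates.

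**Sample counts after the reaction.** A reactor who stops has the 20-30 hour, Early Termination and 4-month samples, plus those at 8 and 12 months if no Milestone for Study End has been triggered: 3 to 5. This leaves out the 8-week visit, because the merged column in the supplied table does not show whether ADA is drawn there. A reactor who continues has 2, or 1 if the reaction follows the last dose.

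**The last-dose case.** Protocol 9.1.1 caps reactor participation at 36 months, which is 24 + 12. That total is reached only if a patient reacting at Month 24 goes on into 12 months of further visits. Table 2 offers those visits only to discontinuers. SAP section 6 ends the treatment period of a patient who completes on-study treatment at the 20-30 hour assessment after the last dose. A later contact with a patient who continues therefore belongs to no defined analysis period.

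**The case against.** **The product labels may settle it.** Dosing, precautions and discontinuation requirements are delegated to the US and Canadian labels, which cannot be checked here. If they call for stopping after a reaction, few patients are affected, and 9.1.1 can be read that way. The restart code in 11.4.3.3 applies to any AE. This stands as a limit on size. It does not remove the conditional wording in 9.1.4 and 9.2.4.4.

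**The protocol text may have moved on.** The SAP cites protocol version 3.0, while the one supplied is version 2.0, so the narrative sections may have been revised. The SAP's own Table 2 and section 6 still carry the restriction.

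**The last-dose case is partly covered.** Protocol 9.1.7 makes the last 4-month follow-up visit of a reactor a study-end milestone, without requiring that the drug was stopped. This shows the intent. No such visit is scheduled for a reactor who continues.

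**The missing column is minor.** Note 7 to SAP Table 2 names the End of Study visit, and protocol 9.2.3.2 requires last-visit ADA in all patients. This is correct: the sample is required by the text, though the table does not show it.

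**Stronger readings that the documents do not support.** A reader might infer that a continuing reactor has no follow-up at all. Table 2 keeps that patient on the 4-monthly visits, with vital signs, immunoglobulins, inflammatory markers and post-injection AEs. A reader might also infer that the summary by ADA status would describe only those who stopped. SAP 8.1 summarises ADA on the safety set, and continuing reactors have baseline and 20-30 hour samples, so they are included. Nor is a full 4-, 8- and 12-month series guaranteed to anyone, because the last two points depend on the milestones even for those who stop.

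**Conclusion.** The inconsistency is real and should be corrected. It is narrower than a general loss of follow-up.

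- **Follow-up:** for a continuing reactor, the 4-month minimum is nominally met for a reaction at any study visit except the last. It fails at the last study dose, or when the reaction is too late for another visit about 4 months on.
- **ADA:** after the 20-30 hour sample, one sample remains at most. It covers no more than one of the three post-reaction points with a Month 12 last visit, and none for reactions at Months 0, 4 or 8 with a Month 24 last visit.
- **Analysis:** continuing reactors stay in the ADA summary, with fewer post-reaction samples than those who stop.

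This rests on three assumptions: at least some reactors continue TEGSEDI, which the documents neither state nor exclude; reactions follow study-visit doses; and protocol version 3.0 does not already resolve the point. The number of patients affected cannot be estimated from the documents.

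**What to change.** Reconcile protocol 9.1.1, 9.1.3, 9.1.4, Table 2 and SAP section 6 by stating which schedule applies to a reactor who remains on TEGSEDI. The wording should neither set nor imply a stopping rule.

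For these patients:
- Draw a pre-injection ADA sample at the 4-monthly visits that remain after the reaction, within the 12 months the plan already sets for reactors.
- When the reaction follows the last study dose, provide the 4-month follow-up contact the protocol already promises, and state in the SAP which analysis period it belongs to.
- Show the End of Study visit in Table 2.
- Do not require 8- and 12-month visits beyond the patient's scheduled participation.

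**Effect.** With a Month 12 last visit, a Month 0 reaction then has ADA at 4, 8 and 12 months, a Month 4 reaction at 4 and 8, and a Month 8 reaction at 4.

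**Cost.** Wording in both documents, and extra ADA tubes at visits where blood is already drawn. With a Month 12 last visit this is 2, 1 or 0 tubes for reactions at Months 0, 4 or 8. With a Month 24 last visit it is at most 3, since the visits at 4, 8 and 12 months after the reaction may all precede the last-visit sample. An occasional 4-month visit after a last-dose reaction is the only new visit.

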## 7 Outcome Variables

Outcomes are measured by reported AEs, changes in vital signs and cytokines/inflammatory markers over a 24 hour interval post-injection of TEGSEDI.

## 8 Statistical Methods

For this phase IV study, only descriptive analyses will be provided. No hypothesis testing will be done. However, 95% confidence intervals will be provided where indicated using the Clopper-Pearson method. Descriptive statistics will comprise the number of observations (n), mean, standard deviation (SD), standard error (SE) of mean, median, minimum, and maximum for continuous variables, and n and percent for categorical variables.

The overall study baseline is defined as the last available observation prior to the first on study TEGSEDI administration.

For each study visit on treatment, changes in vital signs and cytokines/inflammatory markers post-injection of TEGSEDI are calculated relative to the pre-injection values, not relative to the overall baseline values. For visit level summarization, analyses will be performed by the study visit using data as collected in the electronic case report form (eCRF).

### 8.1 Analysis Populations

The safety set includes all patients who received at least one dose of TEGSEDI while enrolled in this study protocol. The safety set will be used in the summary of demographics, medical history, patient disposition, AEs, concomitant medications and ADA (Anti-drug antibody).

The evaluable set includes patients in the safety set having at least one post-dose assessment. The evaluable set will be used in the summaries of AEs by study visit and vital signs and cytokines/inflammatory markers recorded over a 24-hour period.

Listings will be run on the safety set.

### 8.2 Description of Statistical Analyses

#### 8.2.1 Enrollment Disposition and Baseline Information

Summaries using descriptive statistics using the safety set will be provided for:

- Patient disposition

 	
Title: Statistical Analysis Plan
 
Program Name: "A Phase 4 Safety Study Assessing the Adverse Events Occurring Within 24 Hours of TEGSEDI Administration in Patients with polyneuropathy of Hereditary Transthyretin-mediated Amyloidosis (hATTR-PN)"
 
Protocol #: TEG4004
 
[REDACTED]
 
Version: Final 2.0 Effective Date: 06 October 2023

--	---

- Demographics and other baseline characteristics
- Medical history

Patient disposition will be presented by counts and percentages for the completion and discontinuation of the study treatment and for completion of the post-treatment follow-up phase. Medical history will be coded starting with MedDRA (Medical Dictionary for Regulatory Activities) version 22.1 or higher and coding will be re-run periodically using the most recent version of MedDRA. Medical history will be summarized by System Organ Class (SOC) and Preferred Term (PT).

